# 9.4. Data Sources

The Medicare administrative claims database includes individuals  $\geq 65$  years of age and individuals with a qualifying disability who are enrolled in a Medicare FFS plan in the United States. The database includes enrollment information for these individuals and adjudicated claims for inpatient

PFIZER CONFIDENTIAL

CT24-WI-GL02-RF02 6.0 Non-Interventional Study Protocol Template For Secondary Data Collection Study Page 33 of 53 care, ambulatory care, and outpatient prescriptions. Medicare FFS Parts A, B, and D administrative claims data is currently available from 2010 through March 30, 2024 and Medicare Part C data is available from 2015 – 2021. Several studies and systematic reviews have demonstrated the validity of using administrative data in the United States to identify MACE events.

## 9.5. Study Size

To determine the appropriate sample size for our study, we conducted a power analysis based on logrank test. The analysis was designed to evaluate the effect of PCV13 vaccination on the risk of first event MACE, with the following key assumptions:

- Treatment-to-control group allocation ratio: Based on the feasibility study using data from September 14, 2014, to December 31, 2019, the proportion of the vaccinated group is 39.6%. Consequently, the treatment-to-control group allocation ratio was set to 2:3.
- Hazard ratio (HR): We assumed a hazard ratio of 0.85 for the vaccinated group compared to the unvaccinated group, indicating a 15% reduction in the risk of first event MACE associated with PCV13 vaccination. Another scenario with an HR of 0.8 is also provided.
- Hazard rate for control group: Based on the above feasibility study, the 5-year overall event probability was 21.2%. Consequently, we calculated the hazard rate for the control group to be 0.0507. This calculation was derived from the pre-assumed HR of 0.85, the overall 5-year survival probability, and the treatment-to-control group allocation ratio. For the scenario with HR=0.8, the corresponding hazard rate for the control group is 0.0518.
- Follow-up time: In this study, not all patients will complete the full duration of follow-up due to censoring events such as vaccination status switching or death. To account for this in the sample size calculation, we adjusted the calculation using shorter average follow-up periods. Specifically, we considered four follow-up durations: 1-year, 0.75 year, 3 years, and 2.75 years.
- Statistical power: 80%.
- Test was two-sided with significance level (α): 0.05, which corresponds to a 5% chance of a Type I error.

The required total sample sizes for each scenario were determined as follows to achieve a 80% power:

Hazard Ratio	Control Group Hazard Rate	Follow-up time in	Total N Required
		years	
0.85	0.0507	1	27,520
		0.75	36,485
		3	9,600
		2.25	12,585

# Table 6.Sample Size

#### PFIZER CONFIDENTIAL

CT24-WI-GL02-RF02 6.0 Non-Interventional Study Protocol Template For Secondary Data Collection Study Page 34 of 53

0.80	0.0518	1	14,825
		0.75	19,655
		3	5,170
		2.25	6,775

These sample size calculations ensure that the study is adequately powered to detect a clinically meaningful difference in first event MACE risk between the vaccinated and unvaccinated cohorts for both the 1-year and 3-year survival analysis. The TWOSAMPLESURVIVAL statement from the SAS POWER procedure was utilized to conduct sample size calculation for comparing two survival curves using the log-rank test. This analysis was performed using SAS Studio 3.81 (Cary, NC).

### 9.6. Data Management

All Medicare claims structured data described are stored within the Chronic Conditions Warehouse (CCW) Virtual Research Data Center (VRDC). The VRDC is a secure research environment only accessible to approved users listed on Pfizer's Data Use Agreement (DUA) with CMS for the project "Understanding the impact of vaccine-preventable diseases and vaccine uptake in Medicare Fee for Service and Medicaid populations". Data are queried and analyzed using SAS, Structured Query Language (SQL), and R, with the latter two languages accessed through the Databricks Platform.

No patient level data will be removed from the VRDC, only aggregate patient counts will be exported. In addition, patient counts containing a value of 1 to 10 will be censored in accordance with CMS cell size suppression policies.

### 9.7. Data Analysis

The analyses will be conducted separately at 1 year and 3 years of follow-up.

Descriptive statistics will be used to summarize baseline characteristics by vaccination group before and after propensity score weighting. Categorical variables will be summarized using frequency counts and percentages. Continuous variables will be summarized using mean, standard deviation, median, 25th and 75th percentile, minimum, and maximum.

Detailed methodology for summary and statistical analyses of data collected in this study will be documented in a statistical analysis plan (SAP), which will be dated, filed, and maintained by the sponsor. The SAP may modify the plans outlined in the protocol; any major modifications of primary endpoint definitions or their analyses would be reflected in a protocol amendment.

# **Balancing and Covariate Adjustment Methods**

The analysis will utilize inverse probability of treatment weighting (IPTW) to adjust for differences in the baseline characteristics between the PCV13 vaccinated and PCV13 unvaccinated cohorts. IPTW creates a pseudo-population in which the distribution of measured baseline covariates is independent of treatment assignment, thereby mimicking randomization.

Propensity scores (PS) will be created using a logistic regression model and used to calculate the inverse probability of treatment weights. Standardized mean differences (SMD) will be used to assess covariate balance before and after weighting. An absolute standardized difference less than or equal to

#### PFIZER CONFIDENTIAL

CT24-WI-GL02-RF02 6.0 Non-Interventional Study Protocol Template For Secondary Data Collection Study Page 35 of 53 0.1 will be considered as balanced. Stabilized weights will be used to limit the impact of outliers and truncation at the 1st and 99th percentiles may be considered. Covariates with residual imbalance after weighting will be included in the final models for further adjustment to control for potential confounders. Depending on the balance checks for censoring status within the IPTW-weighted population, IPTW may be combined with inverse probability of censoring weighting (IPCW) to address potential issues of informative censoring. IPCW adjusts for potential biases due to censoring, with weights calculated based on the probability of censoring at various time points.

Only baseline covariates will be adjusted for using IPTW. Time-varying influenza vaccination status will be adjusted for directly in the Cox proportional hazards models for the primary outcomes analysis. Individuals will be classified as vaccinated starting 15 days after their first claim for an influenza vaccine during each respiratory season and considered vaccinated until the end of that respiratory season. The Cox model will treat influenza vaccination as a time-varying variable using a counting process. Baseline covariates included in the PS models for IPTW and IPCW will be finalized based on their clinical and statistical importance and will be detailed in the SAP.

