### 9.3.5. Covariates

#### Table 5.Covariates

Variable	Role	Operational definition	Measurement period
Age	Patient characteristics	
 
The number of years between the index date and the patient birth year for each time segment. Age will be reported overall and in the following categories: 65-69 years, 70-74 years, 75-79 years, 80-84 years, and 85+ years.
 
Continuous statistics including mean, standard deviation (SD), median (Q1-Q3), minimum, and maximum, will also be summarized.
 
	Baseline
Sex	Patient characteristics	Sex will be reported as Male (1), Female (2), and Unknown (0)	Baseline
Race/ethnicity	Patient characteristics	Self-reported race will be reported as White (1), Black (2), Other (3), Asian (4), Hispanic (5), North American Native (6), and Unknown (0).	Baseline
Geographic region	Patient characteristics	
 
US geographic region will be derived from the patient state and categorized into the following:
 
Northeast – Connecticut, Maine, Massachusetts, New Hampshire, Rhode Island, Vermont, New Jersey, New York, Pennsylvania
 
Midwest – Indiana, Illinois, Michigan, Ohio, Wisconsin, Iowa, Kansas, Minnesota, Missouri, Nebraska, North Dakota, South Dakota
 
South – Delaware, District of Columbia, Florida, Georgia, Maryland, North Carolina, South Carolina, Virginia, West Virginia, Alabama, Kentucky, Mississippi, Tennessee, Arkansas, Louisiana, Oklahoma, Texas
 
	Baseline

PFIZER CONFIDENTIAL

CT24-WI-GL02-RF02 6.0 Non-Interventional Study Protocol Template For Secondary Data Collection Study Page 27 of 53

		
 
West – Arizona, Colorado, Idaho, New Mexico, Montana, Utah, Nevada, Wyoming, Alaska, California, Hawaii, Oregon, Washington
 
Other/unknown – Puerto Rico/ unknown region
 
	
Respiratory season of index	Patient characteristics	The respiratory season of the individual's index date for each time segment.August 2014 – July 2015 August 2015 – July 2016 August 2016 – July 2017 August 2017 – July 2018 August 2018 – July 2019 August 2019 – November 2019	Baseline
Year of index date	Patient characteristics	The year of the individual's index date for each time segment. 2014, 2015, 2016, 2017, 2018, 2019.	Baseline
Month of index date	Patient characteristics	The month of the individual's index date for each time segment. January, February, March, April, May, June, July, August, September, October, November, or December.	Baseline

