Physical/wellness visit	Patient characteristics	A CPT or diagnosis code for a wellness visit in the 365 days prior to index.	Baseline
Number of hospitalizations in the prior 180d	Patient characteristics	
 
Count of unique days with an acute hospital admission in the 180 days prior to index
 
Dichotomous, yes/no
 
Continuous statistics including mean, standard deviation (SD), median (Q1 Q3), minimum, and maximum
 
	Baseline
Number of outpatient visits in the prior 180d	Patient characteristics	Count unique days with an outpatient visit in the 180 days prior to index	Baseline
		
 
Dichotomous, yes/no
 
Continuous statistics including mean, standard deviation (SD), median (Q1 Q3), minimum, and maximum
 
	
Nursing home stay	Patient characteristics	Any claim with care location of nursing home in the 365 days prior to index.	Baseline
Skilled nursing facility (SNF) stay	Patient characteristics	Any claim with care location of SNF in the 365 days prior to index.	Baseline
Influenza vaccine	Patient characteristics	Baseline influenza vaccination status: One claim (NDC or CPT) for influenza vaccine of any type in the 365d prior to index.	Baseline and follow-up
		Time-varying influenza vaccination status during follow-up : Patients will be identified and can transition between periods of influenza vaccine exposure and non-exposure throughout the study period. Individuals will be classified as vaccinated starting 15 days after their first claim for an influenza vaccine during each respiratory season and considered vaccinated until the end of that respiratory season.	

CT24-WI-GL02-RF02 6.0 Non-Interventional Study Protocol Template For Secondary Data Collection Study Page 31 of 53

		The 1-year mediation analysis will adjust for baseline influenza vaccination status only.	
Type of index influenza vaccine administered	Patient characteristics	Categories include: Enhanced, standard, and unknown influenza vaccine type	Baseline
PPSV23 receipt	Patient characteristics	One claim (NDC or CPT) for a PPSV23 vaccine between 1 year and 5 years prior to the index date.	Baseline
Respiratory failure	Patient characteristics	Any code (any setting) within the prior 365 days for respiratory failure. Prior respiratory failure will be included as a descriptive variable only.	Baseline
Influenza infection	Patient characteristics	≥1 ICD-9-CM or ICD-10-CM code for influenza in 365 days prior to index	Baseline

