### **Primary Outcome Analysis**

The weighted cumulative incidence function (CIF) will be estimated to describe and account for mortality as a competing risk of MACE. This approach provides a non-parametric estimate of the cumulative incidence function, accounting for the competing risk events. The crude weighted CIF will be presented with the log-rank test to compare the CIF curve between the PCV13 vaccinated and PCV13 unvaccinated cohorts.

A cause-specific Cox proportional hazards model with a time-varying covariate for influenza vaccination status and a time-segment approach to PCV13 vaccination status will be used for the primary analysis. The cause-specific cox model will be used to estimate hazard ratios (HRs) for the first event of each MACE outcome, comparing PCV13 vaccinated with PCV13 unvaccinated Medicare beneficiaries. The model accounts for the possibility of competing risks by focusing on the cause-specific hazard. A time segment approach will be used to account for changes in PCV13 exposure status during follow-up, allowing adults who receive PCV13 during the study period to contribute a PCV13 unvaccinated and a PCV13 vaccinated time segment to the study.

For the any MACE outcome model, individuals are censored after experiencing their first MACE event during a given time segment, irrespective of whether the MACE event is myocardial infarction, stroke, or heart failure. The remaining models examine each type of MACE separately and experiencing one type of MACE event (i.e., myocardial infarction) is not a censoring criterion for the other types of MACE outcomes (i.e., stroke or heart failure) during a given time segment.

The HR for PCV13, with a 95% confidence interval, will be calculated over the follow-up period. If the proportional hazards assumption is violated—indicating the effect of PCV13 on the risk of MACE events changes over time—HRs will be estimated for specific follow-up periods (i.e., 0-1 years and 0-3 years).

[figure not shown]

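### Influenza status resets every 1 August and the primary Cox model has no current-calendar term, so the influenza coefficient can absorb seasonality and bias the PCV13 hazard ratio slightly, in a direction that depends on undocumented inputs

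*Protocol*

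**What the plan says.** Section 9.7 (Balancing and Covariate Adjustment Methods) and the influenza row of Table 5 (Section 9.3.5) start influenza-vaccinated status 15 days after the earliest claim of each respiratory season. The person is then "considered vaccinated until the end of that respiratory season. The Cox model will treat influenza vaccination as a time-varying variable using a counting process". Table 5 lists the seasons as "August 2014 – July 2015 August 2015 – July 2016" and so on, so status drops back to unvaccinated on 1 August each year.

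The primary analysis (Section 9.7, Primary Outcome Analysis) is "A cause-specific Cox proportional hazards model with a time-varying covariate for influenza vaccination status and a time-segment approach to PCV13 vaccination status". No other time-varying term is named. Follow-up ends 365 or 1095 days after index (Table 4).

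Calendar time appears only as baseline variables: season, year and month of index, the last defined as "The month of the individual's index date for each time segment". Section 9.7 adds: "Only baseline covariates will be adjusted for using IPTW". Baseline influenza vaccination is also listed: "One claim (NDC or CPT) for influenza vaccine of any type in the 365d prior to index". The final propensity-score list is left to the SAP. The stated route for further model terms is "Covariates with residual imbalance after weighting will be included in the final models for further adjustment to control for potential confounders".

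**The concern.** Under this coding, vaccinated person-time covers late autumn to July, while unvaccinated person-time holds an excess of August to October. On a time-since-index scale, people in the same risk set are in different calendar months. Influenza status is then partly a marker of season, and its coefficient takes up whatever seasonal variation MACE has. Balancing month of index between the arms does not prevent this, because current calendar month still varies within each risk set.

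If the arms also differ in influenza uptake, an influenza coefficient that is too high is offset in the PCV13 coefficient. Where MACE peaks in winter and uptake is higher among PCV13 recipients, the offset favours PCV13, which is the direction of the study hypothesis. The sample is so large that even a shift well under 1% may not be covered by the confidence interval.

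**Working it through.** **The plan's own figures.** The protocol states no figure for this bias. Its control hazard solves 0.4·exp(−0.85·5λ) + 0.6·exp(−5λ) = 1 − 0.212. At λ = 0.0507 the left side is 0.4 × 0.8061 + 0.6 × 0.7760 = 0.788, as required. The log-rank sample size for HR 0.85 at 1 year recomputes to 27,571 (Lakatos method) against the stated 27,520. These figures are used below only for the standard error.

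**Inputs.** From the protocol: the status rule, August-July seasons, 2:3 allocation, hazard 0.0507 and about 25 million eligible people. Assumed, because the protocol does not give them:
- a sinusoidal MACE hazard peaking in mid-January, with peak-to-trough ratio r
- yearly influenza uptake by arm
- doses centred on mid-October, so status is on for about 9 months (November-July) and off for 3 (August-October)
- index dates spread evenly and equally in both arms
- true HR of 1 for both vaccines.

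**Hand check, r = 1.2, uptake 75% (PCV13) v 55% (none).**
1. Amplitude a = (1.2 − 1)/(1.2 + 1) = 0.0909.
2. Mean of the cosine over November-July: (sin 135°/2.356) × cos 60° = 0.150. Over August-October: (sin 45°/0.785) × cos 240° = −0.450.
3. Mean relative hazard of a yearly vaccinee: status on, 1 + 0.0909 × 0.150 = 1.0136; status off, 1 − 0.0909 × 0.450 = 0.9591. For someone never vaccinated it is 1.
4. Pooled uptake: 0.4 × 0.75 + 0.6 × 0.55 = 0.63. Unvaccinated time from yearly vaccinees is 0.63 × 0.25 = 0.1575; from the never-vaccinated it is 0.37. The vaccinees' share is 0.1575/0.5275 = 0.299, so the mean hazard in unvaccinated time is 1 − 0.299 × 0.0409 = 0.9878.
5. Apparent influenza HR = 1.0136/0.9878 = 1.026.
6. The arms differ in vaccinated share of time by 0.20 × 0.75 = 0.15, so log PCV13 HR ≈ −0.15 × ln 1.026 = −0.0039, an HR of about 0.996.

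**Large-sample Cox solution** (expected partial-likelihood score, null for both vaccines, even index dates). The 1-year and 3-year values agree:

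| Uptake, PCV13/none | r = 1.2 | r = 1.5 |
|---|---|---|
| 70/65% | 0.9991 | 0.9979 |
| 75/55% | 0.9964 | 0.9920 |
| 85/45% | 0.9925 | 0.9835 |

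The fitted influenza HR is about 1.03 at r = 1.2 and 1.06 at r = 1.5. Variants with doses spread differently and gaps of 3 to 30 points give about 0.990-0.9995 for PCV13 and 1.02-1.05 for influenza. The 85/45% row is a wider gap than that range.

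**What changes the answer.**
- Equal uptake: PCV13 HR 1.000.
- Lower uptake in the PCV13 arm (45/65%): 1.003 (r = 1.2) to 1.007 (r = 1.5).
- A summer peak (75/55%, r = 1.3): 1.005.
- All index dates of both arms in 14 September-31 October: 0.9988-0.9999 over the table's settings.
- Only the unvaccinated arm clustered there: about 0.995-0.998.
- No influenza term, balanced index dates: 1.000.
- Influenza status carried all year: 1.000, which places the cause in the 1 August reset.

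**Against sampling error.** SE of log HR ≈ 1/√(0.24 × D), where D is the number of events. At 25 million and 1 year, D = 25,000,000 × (1 − e^−0.0507) = 1.236 million and SE = 0.0018. At 3 years, D = 3.527 million and SE = 0.0011. With the influenza term fitted, the values for 75/55% are 0.00187 and 0.00111. A shift of 0.0036 (75/55%, r = 1.2) is then 1.9 SE at 1 year and 3.2 SE at 3 years. A shift of 0.0009 (70/65%, r = 1.2) is below one SE at both. At the protocol's required 27,520 people, D = 1,360 and SE = 0.055, so no such shift would be visible.

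**The case against.** A reader might infer that the model necessarily pushes the PCV13 HR below 1. The documents do not support that. They give no seasonality of MACE, no influenza uptake by PCV13 status and no distribution of index dates. Baseline influenza vaccination is available for weighting, or for the model if still imbalanced, and this would narrow the uptake gap by an unknown amount.

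The unvaccinated index date is the earliest claim after 14 September 2014, which points to clustering in autumn 2014. That nearly removes the bias only if both arms cluster. PCV13 index dates are vaccination dates, allowed up to 30 November 2019.

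A reader might also infer that adjusting for influenza vaccine does more harm than good. That holds only if influenza vaccine has almost no effect on MACE, and Section 7 cites evidence that it lowers the risk. With an assumed true influenza HR of 0.90, a seasonal swing of ±10-15% and uptake of 65/50% or 75/45%, the null PCV13 HR is 0.976-0.988 without the term and 0.990-0.997 with it. The planned adjustment is then incomplete, not counterproductive.

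Two further points stand in part. The Cox time scale is not stated outright; time since index is inferred from the follow-up limits in Table 4. The SAP, not shown here, may add a calendar term. Still, the influenza coding and the named terms of the primary model are fixed in the protocol, and what it delegates explicitly is the baseline covariate list. Finally, the standard errors above use all 25 million people with full follow-up, and ignore early censoring and variance added by weighting. The multiples of SE are therefore upper figures.

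**Conclusion.** The point holds in conditional form. As written, the model lets the influenza coefficient absorb seasonality. It can bias the PCV13 HR below 1 if MACE peaks in winter, influenza uptake stays higher in PCV13 recipients after weighting, and at least the PCV13 arm's index dates are spread over the year. Under the assumed inputs the shift is roughly 0.05% to 1%, far below the 15% reduction used for planning. It would not create or hide an effect of that size. It matters because at full sample size the interval may be narrow enough to exclude 1 under the null. The influenza HR itself is biased upward under a winter peak even when uptake is equal, so the adjustment does not fully do its job. This is a worthwhile, inexpensive improvement and does not invalidate the analysis.

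**What to change.** Split the counting-process records at calendar-month (or quarter) boundaries. Stratify the baseline hazard by current calendar month and year, or adjust for them, in both the 1-year and 3-year models. Keep the influenza status as defined. State the Cox time scale in the same sentence. Within a calendar stratum the null hazard depends on neither vaccine, so both HRs return to 1.000 in the calculation above. Cohort, exposure and outcome definitions do not change. The cost is more rows to process in a dataset already planned in counting-process form.

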### **Primary Outcome Analysis**

The weighted cumulative incidence function (CIF) will be estimated to describe and account for mortality as a competing risk of MACE. This approach provides a non-parametric estimate of the cumulative incidence function, accounting for the competing risk events. The crude weighted CIF will be presented with the log-rank test to compare the CIF curve between the PCV13 vaccinated and PCV13 unvaccinated cohorts.

A cause-specific Cox proportional hazards model with a time-varying covariate for influenza vaccination status and a time-segment approach to PCV13 vaccination status will be used for the primary analysis. The cause-specific cox model will be used to estimate hazard ratios (HRs) for the first event of each MACE outcome, comparing PCV13 vaccinated with PCV13 unvaccinated Medicare beneficiaries. The model accounts for the possibility of competing risks by focusing on the cause-specific hazard. A time segment approach will be used to account for changes in PCV13 exposure status during follow-up, allowing adults who receive PCV13 during the study period to contribute a PCV13 unvaccinated and a PCV13 vaccinated time segment to the study.

For the any MACE outcome model, individuals are censored after experiencing their first MACE event during a given time segment, irrespective of whether the MACE event is myocardial infarction, stroke, or heart failure. The remaining models examine each type of MACE separately and experiencing one type of MACE event (i.e., myocardial infarction) is not a censoring criterion for the other types of MACE outcomes (i.e., stroke or heart failure) during a given time segment.

The HR for PCV13, with a 95% confidence interval, will be calculated over the follow-up period. If the proportional hazards assumption is violated—indicating the effect of PCV13 on the risk of MACE events changes over time—HRs will be estimated for specific follow-up periods (i.e., 0-1 years and 0-3 years).

[figure not shown]

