# 9.3.4. Censoring

### Table 4.Censoring Variables

Variable	Role	Operational definition	Measurement period
Outcome under study	Censoring	See outcome table above. Table 2.	Follow-up
Disenrollment	Censoring	The month an individual disenrolls from the insurance plan, as indicated in the Master Beneficiary Summary File. Disenrollment date is calculated as the maximum date of enrollment.	Follow-up
Death	Censoring	Date of death reported in the database.	Follow-up
End of study period	Censoring	December 31, 2019	Follow-up
End of follow-up	Censoring	365 days after the index date for the 1- year analysis and 1095 days after the index date for the 3 year analysis.	Follow-up
PPSV23 receipt	Censoring	1 CPT or NDC code for PPSV23 vaccination during follow-up.	Follow-up
PCV13 receipt	Censoring	1 CPT or NDC code for PCV13 receipt during unvaccinated follow-up.	Follow-up
		1 CPT or NDC code for receipt of a second PCV13 vaccine during vaccinated follow-up.	

PFIZER CONFIDENTIAL

CT24-WI-GL02-RF02 6.0 Non-Interventional Study Protocol Template For Secondary Data Collection Study Page 26 of 53

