# Sensitivity Analysis

The study will include three sensitivity analyses. The first sensitivity analysis will use the Fine-Gray model to assess the robustness of the HRs. The Fine-Gray model is a subdistribution hazards model, which evaluates of the effect of covariates on the CIF for each competing risk outcome separately. This model provides an alternative to the cause-specific Cox model and helps ensure the robustness of the findings against an alternative analytical approach for examining competing risks. Second, the study will incorporate a sensitivity analysis to examine an alternative definition of stroke. The primary analysis will include ischemic stroke only and the sensitivity analysis will include hemorrhagic and ischemic stroke. The stroke sensitivity definition will only be examined for the objective assessing the effect of PCV13 on the risk of stroke. The third sensitivity analysis will modify the definition of CAP in the mediation analysis to only include CAP cases with a diagnosis code in the hospital setting. A separate analysis of CAP cases in the outpatient or other non-hospital settings may be considered. Additional details will be provided in the SAP.

PFIZER CONFIDENTIAL CT24-WI-GL02-RF02 6.0 Non-Interventional Study Protocol Template For Secondary Data Collection Study Page 37 of 53

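### The log-rank test named for comparing the weighted cumulative incidence curves tests MACE cause-specific hazards, so its p-value need not match the curves if mortality differs by vaccination status

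*Protocol*

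**What the plan says.** All places are in the Protocol.

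- **Section 9.7, Primary Outcome Analysis**, gives the reason for the CIF: "The weighted cumulative incidence function (CIF) will be estimated to describe and account for mortality as a competing risk of MACE". The same paragraph names the test: "The crude weighted CIF will be presented with the log-rank test to compare the CIF curve between the PCV13 vaccinated and PCV13 unvaccinated cohorts".
- **Section 9.3.4, Table 4**, lists death among the censoring variables, defined as "Date of death reported in the database".
- **Section 9.7, Primary Outcome Analysis**, makes a cause-specific Cox model the primary analysis: "The model accounts for the possibility of competing risks by focusing on the cause-specific hazard".
- **Section 9.7, Sensitivity Analysis**, plans one regression on the CIF scale: "The Fine-Gray model is a subdistribution hazards model". It is the first of three sensitivity analyses.

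No test of equality of CIFs, such as Gray's test, is named anywhere in the protocol.

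**The concern.** The plan chooses the CIF so that deaths are not treated as ordinary censoring, then attaches to it a test that does treat them so. The two answer different questions. The CIF gives the probability of having had MACE by a given time when people can die first. The log-rank with deaths censored asks whether the MACE rate among those still alive and event-free is the same in both cohorts, which is the question the primary Cox model already asks.

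If mortality differs by vaccination status, curves could separate beside an unremarkable p-value, or lie together beside a small one. A reader of the figure would take the p-value as a statement about the curves. At stake is the interpretation of that display, not the primary estimate.

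**Working it through.** **1. The plan's own figures.** Section 9.5 states: "We assumed a hazard ratio of 0.85 for the vaccinated group compared to the unvaccinated group". With 2:3 allocation and a 5-year overall event probability of 21.2%, the control hazard h solves

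0.6 × (1 − e^(−5h)) + 0.4 × (1 − e^(−5 × 0.85h)) = 0.212,

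which gives h = 0.0507, as stated. A Lakatos-type log-rank calculation (two-sided 0.05, 80% power) gives 27,571 at 1 year and 9,615 at 3 years, against the stated 27,520 and 9,600. All eight entries of Table 6 reproduce within 0.2%. The sizing is sound for a log-rank test of hazards and is not in question.

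**2. Why the two hypotheses differ.** With constant MACE hazard λ1 and death hazard λ2,

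CIF(t) = λ1 / (λ1 + λ2) × [1 − e^(−(λ1 + λ2)t)].

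The log-rank with deaths censored depends on λ1 only in its null hypothesis. The CIF depends on both hazards.

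**3. Size of the gap when the MACE hazards are equal.** Inputs: λ1 = 0.0507 in both groups (from Section 9.5). Assumptions, because the protocol gives no death rates: λ2 = 0.02, 0.05 or 0.08 per year in the unvaccinated, and a death hazard ratio of 0.8.

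Example, λ2 = 0.05 against 0.04, at 3 years:
- unvaccinated: 0.0507/0.1007 × (1 − e^(−0.3021)) = 13.13%
- vaccinated: 0.0507/0.0907 × (1 − e^(−0.2721)) = 13.32%
- difference: 0.19 percentage points

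| Death hazard, unvaccinated | CIF gap, 1 year (points) | CIF gap, 3 years (points) |
|---|---|---|
| 0.02 | 0.01 | 0.08 |
| 0.05 | 0.02 | 0.19 |
| 0.08 | 0.04 | 0.29 |

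The cause-specific hazard ratio is 1 in every row, so the log-rank is at its null throughout.

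**4. When such a gap is detectable.** Simple z = difference / √[a(1−a)/(0.6N) + b(1−b)/(0.4N)], where a and b are the two CIFs. This assumes complete follow-up and no weights, so it is optimistic.

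| Death hazard | 3 years, N = 9,600 | 3 years, N = 1 million | 3 years, N = 10 million | 1 year, N = 10 million |
|---|---|---|---|---|
| 0.02 | 0.1 | 1.1 | 3.6 | 0.7 |
| 0.05 | 0.3 | 2.7 | 8.6 | 1.7 |
| 0.08 | 0.4 | 4.2 | 13.3 | 2.7 |

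**5. Simulation of the two tests.** Ordinary log-rank (deaths censored) against a Gray-type test (deaths kept in the risk set), unweighted, 3 years, death hazard 0.05, N = 200,000. Rejection rates at two-sided 0.05 are approximate:

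| Scenario | Log-rank | Gray-type |
|---|---|---|
| MACE HR 1, death HR 1 | 4.5% | 4.5% |
| MACE HR 1, death HR 0.8 | 5% | 21% |
| MACE HR 1, death HR 0.6 | 4.5% | 71.5% |
| 3-year CIFs equal (MACE HR 0.985), death HR 0.8 | 21.5% | 5.5% |
| 3-year CIFs equal (MACE HR 0.970), death HR 0.6 | 56% | 4.5% |

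The tests agree when mortality is the same and part in both directions when it is not. At the minimum N = 9,600 over 3 years, with MACE HR 1 and death HR 0.8, they reject in 4.2% and 5.1%, which is no practical difference.

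**The case against.** The strongest reply is that little depends on this p-value. The primary result is the cause-specific Cox hazard ratio with its confidence interval, and the log-rank is coherent with that. The Fine-Gray model already covers the CIF scale. No decision rule, alpha or sample size uses the curve comparison. All of this stands, and it limits the consequence to one displayed p-value. It does not make the sentence correct, because the sentence says what the test compares.

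Three stronger readings are tempting, and the document does not support them.

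- **That the p-value will disagree with the curves.** It need not agree. The disagreement depends on how far mortality differs, and it is trivial at 1 year or at the planned minimum sizes. Equal MACE hazards of 0.05 with death hazards of 0.05 and 0.03 give 12.96% against 13.34% at 3 years, about 27 standard errors with 10 and 15 million people. That is arithmetically right but a single favourable case: a death hazard ratio of 0.6, all 25 million eligible people, no weights and full 3-year follow-up. Index dates run to 30 November 2019, the study ends on 31 December 2019, and segments are censored at vaccine receipt and disenrollment, so many cannot reach 3 years.
- **That the plan expects lower mortality in the vaccinated.** The Negative Control Outcomes text says only that residual confounding from healthy-vaccinee behaviour will be explored. It says nothing about mortality, and the curves are weighted to reduce baseline differences. A mortality difference is plausible, not stated.
- **That the test uses the wrong variance under estimated weights.** The protocol names no variance for it, and Section 9.7 leaves detailed methodology to the SAP. This is not a fault of the document.

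**Conclusion.** The point holds in a limited form. The protocol names, as the comparison of the CIF curves, a test whose null hypothesis concerns cause-specific hazards, and it names no test of CIF equality. This is a stated rule, not a detail deferred to the SAP.

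Under the assumed death hazards and a death hazard ratio of 0.8, the mismatch is worth 0.08 to 0.29 points of 3-year CIF and 0.01 to 0.04 points at 1 year. It cannot be seen at the minimum sample sizes. At 3 years it passes the conventional threshold in all three scenarios with 10 million people, and with 1 million in the two with the higher death hazards. These figures rest on constant hazards and on death rates that the protocol does not give. If mortality does not differ by vaccination status, the problem has no practical effect. It should be corrected because the correction is cheap and the cohort is large enough for small gaps to matter.

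**What to change.** Change one sentence in Section 9.7, Primary Outcome Analysis. Replace the log-rank as the CIF comparison with one of the following:

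- the weighted CIF difference at 1 and 3 years with robust or bootstrap confidence intervals, which also shows the size of the difference;
- a weighted Gray-type test;
- the test of PCV13 in the Fine-Gray model already planned, fitted with the same weights.

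If the log-rank is kept, describe it as a test of cause-specific hazards and do not attach it to the CIF curves.

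No new data are needed, and neither alpha nor the sample size changes. Using the Fine-Gray test adds no new model. The CIF difference or the Gray-type test adds a small amount of programming.
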